## 4.0 ENDPOINTS

The following endpoints chosen for the post market clinical follow-up evaluation are the recognized professional and industry standards in determining performance of drug eluting stents in interventional cardiology.

- Acute Device Success: attainment of final result with < 50% residual stenosis of the target site, using a DESyne X2 stent and standard pre-dilation catheters and post-dilatation catheters (if applicable)

Physician feedback will be obtained for the following device characteristics:

- Device preparation
- Lesion access and cross
- Stent expansion
- Delivery system removal
- Stent crossability for post-dilatation as required
- Device malfunction assessment

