#### 3.2 Inclusion Criteria

Candidates for this study must meet all of the following criteria:

- 1) The patient must be  $\geq 18$  years of age
- 2) Patient is able to verbally confirm understanding of risks, benefits and treatment alternatives of receiving the DESyne X2 NECSS and he/she provides written informed consent, as approved by the appropriate Ethics Committee of the respective clinical site, prior to any clinical study related procedure
- 3) The patient must have stable angina pectoris as defined by the Canadian Cardiovascular Society Classification, documented silent ischemia, acute coronary syndrome, or a positive functional study requiring treatment
- 4) The patient is considered a candidate for coronary stent implantation and has a planned intervention of up to three lesions located in separate major epicardial territories. Each lesion/vessel must meet the following criteria:
  - a. *De novo* lesion
  - b. The target lesion reference site must be visually estimated to be  $\geq 2.25$  mm and  $\leq 4.0$  mm in diameter\*
  - c. The target vessel must be a major coronary artery or major branch with a visually estimated stenosis of  $\geq 50\%$  and  $<100\%$ .
  - d. The visually estimated target lesion length must be  $\leq 34$  mm\*  
 $\geq$  TIMI 1 coronary flow

\*Subject to commercial availability of product sizes in the specific region/country

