#### **3.5.2 Catheterization and Stenting Procedure**

The stenting procedure will follow standard procedures for balloon angioplasty and shall be in accordance with the Instructions for Use packaged with each DESyne X2 stent. The available stent diameters are 2.25 mm, 2.75 mm, 3.0 mm, 3.5 mm, and 4.0 mm with stent lengths of 14 mm, 18 mm, 23 mm, 28 mm, 32 mm, and 38 mm lengths. Pre-dilate the lesion using a balloon that is shorter in length than the planned DESyne X2 stent length. Deploy the stent slowly until the stent is completely expanded. Maintain pressure for 30 seconds. Direct stenting is not recommended.

- Should any resistance be felt at any time during either lesion access or removal of the delivery system post stent implantation, the entire system should be removed as a single unit (See appropriate IFU for further information).
- According to the IFU, stent expansion should not exceed the RBP of 16 atm and the stent should not be expanded beyond 0.5 mm over the nominal diameter.

Evaluate the lesion via angiography. If an optimal angiographic result has still not been achieved using the coronary stent system, additional balloon inflations using an appropriately sized, non-compliant balloon may be performed.

[figure not shown]
The stenting procedure will include a single lesion treatment in a single epicardial vessel or a single lesion treatment in up to three separate major epicardial territories.

Maintain a copy of all of the index procedure angiographic images for possible analysis by an independent angiographic core laboratory.

---

 Not all sizes available in all regions. Subject to commercial availability. Availability is based on regulatory and hospital approvals.

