### Flowchart for Treatment of Two Lesions in Two Separate Epicardial Territories

#### Optimal lesion/vessel treatment is defined as:

- a. < 20% residual stenosis by visual assessment
- b. no evidence of dissection
- c. no evidence of thrombus in the target lesion or vessel
- d. TIMI 3 flow

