### 3.5.7 Other Follow-up Guidelines

There may be situations where an attempt to treat the patient with the DESyne X2 stent is made, but the procedure is stopped prior to the stent being delivered to the target site (i.e., the stent is introduced into the guiding catheter and circulation but patient becomes unstable, power outage, etc.). In these situations, the patient will be deregistered from the study and treated per standard hospital practice.

In the situation where an attempt to treat the patient with the DESyne X2 stent is made but due to a device malfunction or failure to cross the lesion, no DESyne X2 stent is subsequently implanted, the case shall be noted as not meeting the Device Success endpoint. All device failures will be recorded and reported.

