#### **6.0 STATISTICAL CONSIDERATIONS**

This Post Marketing Clinical Follow-up (PMCF) study is designed to confirm the performance of the DESyne X2 Novolimus Eluting Coronary Stent System with regards to the residual risks of lesion access and acute device implantation through visually-assessed angiographic endpoints and physician feedback and demonstrate that these characteristics are not different than the DESyne Novolimus Eluting CSS. The overall result of this study will be summarized descriptively, and examined relative to the clinical results observed in the EXCELLA II Randomized Study.

Data for all categorical endpoints will be summarized with patient counts, percentages, and exact 95% Clopper-Pearson confidence intervals.

One study population will be examined during the analyses: the modified intent-to-treat population (MITT), which will consist of all patients treated with at least one DESyne X2 stent.

While this post marketing study is not powered to determine extremely rare events, a sample size of 100 patients is sufficient to detect rare, acute device related performance issues.

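### Among patients who receive an X2 stent, Device Success at under 50% residual stenosis is insensitive to the quality of the result, and the protocol's own optimal-result definition is never summarised

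*Combined protocol and SAP*

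**What the plan says.** **Endpoint.** Sections 1.0, 2.6, 4.0 and 9.0 define Device Success as "attainment of final result with < 50% residual stenosis of the target site", reached with an X2 stent together with standard pre- and post-dilatation catheters. It is the only angiographic endpoint listed. The other listed items are device characteristics, stent expansion among them; Sections 2.6, 4.0 and 9.0 collect these as physician feedback.

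**Entry.** Section 3.2 requires "a major coronary artery or major branch with a visually estimated stenosis of" at least 50% and below 100%.

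**Optimal result.** The text with the flowchart in Section 3.5.2, and again Section 9.0, define optimal treatment as "< 20% residual stenosis by visual assessment" plus no dissection, no thrombus and TIMI 3 flow. Section 3.5.2 lets the operator act on it: "If an optimal angiographic result has still not been achieved using the coronary stent system, additional balloon inflations" may be performed with a non-compliant balloon. No endpoint list contains this result, and Section 6.0 does not summarise it.

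**Failures and population.** When malfunction or failure to cross leaves a patient with no X2 stent, Section 3.5.7 says "the case shall be noted as not meeting the Device Success endpoint". Section 6.0 names a single population, the modified intent-to-treat set, "which will consist of all patients treated with at least one DESyne X2 stent".

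**Data.** Section 4.1 lists estimated percent stenosis of the target lesion without saying whether it is taken before or after the procedure. It does not list final TIMI flow, dissection or thrombus.

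**The concern.** The study aims to confirm acute implantation performance through visually judged angiographic endpoints and operator feedback, and to show that X2 is no different from DESyne. Only one endpoint is angiographic. On its stenosis component, a lesion that enters at 50% and finishes at 49% succeeds, exactly as one that finishes at 0% does.

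Once the analysis is confined to patients with an X2 stent in place, most delivery failures have left the denominator, and what remains is chiefly the 50% cut. A similar Device Success rate for X2 and DESyne would then say little about the quality of the final result. The protocol already defines a finer standard, which operators are expected to judge during the case, yet the plan does not report it.

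**Working it through.** Section 6.0 gives a sample size of 100 but no expected rate, benchmark or margin, so there is no figure of the plan's to reproduce for this point. The checks below use n = 100 and label every assumption.

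**1. The two cut-points.** Entry: stenosis ≥ 50%. Success: residual < 50%. The boundary is the same, so any visible fall from the minimum entry value satisfies the stenosis part of the endpoint.

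**2. What the endpoint can show beside the optimal result.** Exact (Clopper-Pearson) limits for x of n are the 2.5% quantile of Beta(x, n−x+1) and the 97.5% quantile of Beta(x+1, n−x). When x = n, the lower limit is 0.025^(1/n) and the upper limit is 100%. For n = 100 this gives 0.025^(0.01) = 96.4%.

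Assume that every patient finishes below 50% and that m of 100 have at least one lesion at 20–49%:

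| m (assumed) | Device Success | All treated lesions < 20% |
|---|---|---|
| 0 | 100/100: 96.4–100% | 100/100: 96.4–100% |
| 5 | 100/100: 96.4–100% | 95/100: 88.7–98.4% |
| 10 | 100/100: 96.4–100% | 90/100: 82.4–95.1% |
| 20 | 100/100: 96.4–100% | 80/100: 70.8–87.3% |

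The Device Success column cannot move, by construction. The table shows what the single cut would hide; it does not predict m.

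**3. How likely such a pattern is.** Assume that final residual stenosis per lesion is normal with mean 5–20% and SD 8–12%. None of this is in the documents, and a normal curve is only a rough shape for a quantity bounded at zero.

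- Mean 5, SD 8: share < 50% is Φ((50−5)/8) ≈ 100%; share < 20% is Φ((20−5)/8) = Φ(1.875) = 97%.
- Mean 10, SD 10: share < 50% ≈ 100%; share < 20% is Φ(1) = 84%.
- Mean 20, SD 12: share < 50% is Φ(2.5) = 99.4%; share < 20% is Φ(0) = 50%.

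Over the six mean and SD pairs tried in this range, 99.4–100% of lesions pass the 50% cut and 50–97% pass the 20% cut.

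**4. What the population does to Device Success.** Suppose that f of 100 attempts end with no X2 stent because of malfunction or failure to cross, and all others succeed:

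- f = 3: all attempts 97/100 (91.5–99.4%); modified intent-to-treat 97/97 (96.3–100%).
- f = 5: all attempts 95/100 (88.7–98.4%); modified intent-to-treat 95/95 (96.2–100%).

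Section 3.5.7 calls these cases failures. The Section 6.0 population removes them.

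**5. Whether a high rate alone removes information.** Take an assumed fixed benchmark and an exact one-sided 0.025 binomial rule at n = 100.

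- Benchmark 99%: a fall is declared at 96 or fewer successes (probability 1.8% if the rate is still 99%). Power at a true 95% is 74%.
- Benchmark 90%: a fall is declared at 83 or fewer (probability 2.1% if the rate is still 90%). Power at a true 85% is 33%.

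A rate near 100% can therefore still reveal a fall, provided that the failures stay in the denominator.

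**The case against.** The strongest reply is that Device Success is more than a stenosis threshold. It requires an X2 stent, and Section 3.5.7 scores malfunction and failure to cross as failures. Those are the delivery-system risks under study, and Section 2.2 says that the stent itself is unchanged from DESyne. Expansion, crossing and removal are also covered by physician feedback. This stands, and it limits the point to the quality of the result among patients with an X2 stent. It does not rescue the planned analysis, because the Section 6.0 population drops patients in whom no X2 stent was implanted.

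A second reply is that the optimal result is procedural guidance, and leaving it out of the endpoints is a design choice. Further inflations are allowed when the result falls short, so a final rate below 20% partly reflects post-dilatation and operator effort. Dissection, thrombus and flow also depend on the lesion and the patient. This stands too. The added figure would describe the implantation result, not the delivery system in isolation, and should be read with post-dilatation use.

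A reader might go further and infer that the study's main endpoint sits at a ceiling and is uninformative. The documents do not support that. They give no expected or historic Device Success rate and name no primary endpoint (Section 1.0 lists key endpoints). Step 5 of the working also shows that a high rate does not by itself prevent a fall from being seen.

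**Conclusion.** The point holds in a limited form and is minor. Three facts rest on the text alone: entry and success share the 50% cut-point, Device Success is the only angiographic endpoint, and the optimal-result definition is neither an endpoint nor summarised. It follows that, in the population to be analysed, Device Success hardly distinguishes a good result from a marginal one.

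The size rests on assumptions. With 5 to 20 of 100 patients having a lesion at 20–49%, Device Success stays at 100% while the proportion with all lesions below 20% runs from 95% down to 80%. A ceiling is likely but not demonstrated. There is no numerical error in the plan here. The conflict between Sections 3.5.7 and 6.0 over device-related non-implants is a separate matter that makes this one worse.

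**What to change.** Keep Device Success at its present cut-point for the comparison with historic DESyne data, and add to it:

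- **Section 4.1:** state that percent stenosis is recorded after the procedure, and add final TIMI flow, dissection and thrombus.
- **Sections 2.6, 4.0 and 6.0:** add as descriptive endpoints (a) the distribution of final residual stenosis, (b) the proportion of patients with all treated lesions below 20%, and (c) the proportion of patients meeting all four parts of the protocol's optimal-result definition. Give exact 95% intervals for (b) and (c).
- **Unit:** count per patient, since Section 6.0 specifies patient counts and Section 3.2 allows up to three lesions. Any lesion-level interval must allow for clustering within patients.
- **Context:** report post-dilatation use beside these figures.

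Separately, reconcile the Section 6.0 population with Section 3.5.7, so that device-related non-implants are handled in the Device Success denominator as Section 3.5.7 requires.

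The cost is one table and a few case report form fields. The drawbacks are a less flattering second figure and, possibly, no historic DESyne counterpart. The second is tolerable because Section 6.0 plans a descriptive summary.

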### 4.1 Lesion, vessel, and stent characteristics

Lesion, vessel, and stent characteristics recorded in the source documentation should include:

- Estimated reference vessel diameter (target lesion)
- Estimated lesion length
- Estimated % DS (target lesion)

- Number of stents used
- Stent brand
- Vessel (LAD, LCX, RCA, Left Main)
- Lesion location (ostial, proximal, mid, distal, branch)
- Stent diameter (mm)
- Stent length (mm)
- Lot number of the DESyne X2 stent
- Success of stent implantation or device malfunction details

**Note:** Maintain a copy of all of the index procedure angiography for possible analysis by an angiographic core laboratory.

#### **4.2 Device and Drug Related Adverse Events**

A list of adverse events which may result from the use of the device, the implant procedure, the drug on the stent, or the use of concomitant procedural drugs are described in the Instructions for Use for each device.

#### **5.0 EARLY WITHDRAWAL FROM THE STUDY**

Following the introduction into the body of the intended device, all patients are considered enrolled into the study. Patients will be exempt from only if they withdraw their consent or the physician withdraws them from the study.

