### 2.6 Study Endpoints

The endpoints for this post-marketing clinical follow-up study include:

- Acute Device Success: attainment of final result with < 50% residual stenosis of the target site, using a DESyne X2 stent and standard pre-dilation catheters and post-dilatation catheters (if applicable)

Physician feedback will be obtained for the following device characteristics:

- Device preparation
- Lesion access and cross
- Stent expansion
- Delivery system removal
- Stent crossability for post-dilatation as required
- Device malfunction assessment

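### Device-preparation failures that end without a DESyne X2 stent fall outside both enrolment and the only analysis population, so any bias in the preparation result runs toward zero

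*Combined protocol and SAP*

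**What the plan says.** - **Endpoint.** Sections 2.6, 4.0 and 9.0 introduce a six-item list. In Section 2.6 it opens with "Physician feedback will be obtained for the following device characteristics", and the first item is "Device preparation". The Protocol Summary places the same items under Key Endpoints. No section defines what counts as a preparation failure.
- **Enrolment.** Section 5.0: "Following the introduction into the body of the intended device, all patients are considered enrolled into the study". The heading of Section 3.5.1 instead places patient enrolment before catheterization, but the text beneath it covers only screening.
- **Analysis.** Section 6.0 names one population, the MITT, "which will consist of all patients treated with at least one DESyne X2 stent". It adds: "Data for all categorical endpoints will be summarized with patient counts, percentages, and exact 95% Clopper-Pearson confidence intervals".
- **Recording of failures.** Section 3.5.4 has failure to implant at the target site entered on the CRF as a treatment failure. Section 3.5.7 says that an attempt ending with no X2 stent, because of malfunction or failure to cross, does not meet Device Success, and that device failures are to be recorded and reported. Section 4.1 asks for the X2 lot number and malfunction details.

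**The concern.** Preparation is finished before the device enters the body. A system that fails on the table and is replaced by another product therefore leaves a patient who never meets the Section 5.0 enrolment condition and never meets the Section 6.0 population condition. The exclusion depends on the outcome being measured, so it cannot average out.

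Section 2.2 names the delivery system as the main difference from the earlier DESyne systems, and Section 2.3 says the attributes under study relate most directly to that updated delivery system. A selection rule that can only hide its failures weakens the confirmation the study is meant to give. Section 6.0 also says 100 patients are enough to detect rare acute device-related performance issues. That cannot apply to failures that never reach the analysis set.

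**Working it through.** **1. The plan's own figure.** Section 6.0 gives N = 100 with no event rate, power or precision, so it cannot be reproduced. What 100 patients offer if every failure is captured is P(at least one) = 1 − (1 − p)^100. This gives 63.4% at p = 1%, 86.7% at 2%, 95.2% at 3% and 99.4% at 5%. These values of p are assumptions; the documents give no preparation failure rate.

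**2. Where each kind of case ends up under the written rules.**

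| Case | Enrolled (5.0) | In MITT (6.0) |
|---|---|---|
| First X2 system fails at preparation, second X2 stent implanted | Yes | Yes |
| X2 system fails at preparation, no X2 stent used | No | No |
| X2 system introduced, malfunction or failure to cross, no X2 stent implanted | Yes | No, yet a Device Success failure under 3.5.7 |

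**3. Size of the selection effect.** Let f be the true share of patients with a preparation failure. Let s be the share of those who still receive an X2 stent and whose failure is recorded. If the rest are lost, the observed rate is f·s / (1 − f·(1 − s)). Both f and s are assumptions. At f = 3%:

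| s | Observed rate | P(at least one seen in 100) |
|---|---|---|
| 0 | 0% | 0% |
| 0.25 | 0.0075/0.9775 = 0.77% | 53.7% |
| 0.5 | 0.0150/0.9850 = 1.52% | 78.4% |
| 0.75 | 0.0225/0.9925 = 2.27% | 89.9% |
| 1 | 3.0% | 95.2% |

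At f = 1% the observed rate runs from 0% to 1.0%, and at f = 5% from 0% to 5.0%. The error is downward or nil in every case.

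**4. Effect on the reported interval.** Assume 100 analysed patients with no recorded preparation failure, plus a few patients lost at preparation, with one opened system per patient. Exact Clopper-Pearson 95% limits, as Section 6.0 specifies:

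- As written: 0/100 = 0%, upper limit 1 − 0.025^(1/100) = 3.6%.
- One lost: 1/101 = 1.0% (0.03% to 5.4%).
- Two lost: 2/102 = 2.0% (0.2% to 6.9%).
- Three lost: 3/103 = 2.9% (0.6% to 8.3%).

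**5. Device Success.** The third row of the table in step 2 needs no assumption about preparation. Section 3.5.7 counts the case as a failure, and Section 6.0 leaves it out of the only population in which a percentage is calculated.

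**The case against.** The strongest reply is that the plan does not ignore device failures. Sections 3.5.4, 3.5.7 and 4.1 require them to be recorded, and Section 7.3 adds screening and issues logs. That stands as far as recording goes, so failures need not vanish from the study file. None of these sections, however, puts the patient into a denominator, and Section 3.5.7 does not say whether an attempt to treat includes preparation.

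A reader might infer that every preparation failure drops out and that the rate is forced to zero. The documents do not support that. A patient whose second X2 system is implanted is enrolled and in the MITT, and the result reaches zero only if no preparation failure is followed by a recorded X2 implant.

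A reader might also infer that the crossability item is diluted by patients who were never post-dilated. The item is worded "Stent crossability for post-dilatation as required", and Section 3.5.2 makes the step optional: "additional balloon inflations using an appropriately sized, non-compliant balloon may be performed". A denominator of post-dilated cases fits that wording, and Section 6.0 does not say otherwise. This is a silence to fill, not a shown error.

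Three further points stand. The enrolment rule sits in a section on early withdrawal and is in tension with the heading of Section 3.5.1. The stated objective names lesion access and acute implantation, not preparation. And because preparation is physician feedback with no failure criterion, treating it as a rate is an inference from the Section 6.0 rule for categorical endpoints. These limit the weight of the point but do not change the direction of the error.

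**Conclusion.** The point holds in a limited form. Preparation failures that end with no X2 stent have no place in enrolment or in the MITT, so the preparation result can only be too favourable or, at best, unaffected. The amount is unknown because the documents give neither a failure rate nor the frequency with which a second X2 system follows. Three lost cases, an assumed number, would turn 2.9% into 0% and lower the upper limit from 8.3% to 3.6%. The conflict between Sections 3.5.7 and 6.0 over Device Success follows from the text alone. The change is worth making before analysis. Crossability needs only a stated denominator.

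**What to change.** In Section 6.0, define an attempted-device set: all consented patients for whom a DESyne X2 system was opened, including systems never introduced. Use it for device preparation, malfunction and Device Success, and keep the MITT for summaries of treated patients.

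Record physician feedback per device rather than per patient, so that a failed first system is counted when a second is implanted. State what counts as a preparation failure. Add one CRF accountability line for opened but unused systems, with lot number and reason.

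Reconcile the heading of Section 3.5.1 with Sections 3.5.7, 5.0 and 6.0 on when a patient is enrolled and who is analysed. Say whether an attempt begins at opening, and where patients deregistered under Section 3.5.7 are shown.

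For crossability, state that the denominator is cases in which post-dilatation was attempted.

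The cost is protocol wording and the CRF line. No patients or procedures are added, and some reported rates will be slightly less favourable.
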